10.1.3 Procedure for handling missing data

The safety assessment will include in the analysis all those patients (both eyes) who have been exposed at least once to the intervention, regardless of the visit at which they were eliminated from the study (ITT).

10.1.4 Deviations from the statistical analysis plan

According to the calculation of the sample size to meet the objective of the study, 50 evaluable patients are required per arm. If this number is not met due to a loss of patients greater than 20% contemplated in this protocol (loss of follow-up or withdrawal of ICF), the sponsor may replace these patients.

The results obtained from the replaced patients will continue to be used for safety analysis and will be part of the ITT.

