4.1 Design Overview

Phase IV non-inferiority, controlled, open-label, comparative, multicenter clinical study.

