4.2 Rationale for the study design

Humylub Ofteno® PF is a product that is currently available for consumption not only in Mexico, but in several Latin American countries such as: Bolivia, Chile, Colombia, Costa Rica, Costa Rica, Colombia, Costa Rica, Colombia Dominican Republic, Ecuador, Guatemala, Haiti, Honduras, Nicaragua, Panama and El Salvador.

Both the efficacy and safety of its compounds, HS and CS, have been proven for use as a treatment for SOS, reducing both the signs and symptoms associated with this pathology. There are several ophthalmic solutions on the market that contain these compounds, including the comparators chosen for this study, Hyabak® and Lagricel® PF. The latter are composed of sodium hyaluronate, at different concentrations, and are also used for the treatment of SOS. One of the main purposes of SOS treatment is to reduce the symptoms described by patients such as burning, SCE, blurred vision, etc. The objective evaluation of these is carried out through internationally approved and accepted questionnaires, which are described in reference documents such as the TFOS DEWS II. One of these tools is the OSDI, the results of which will be considered in this study as the primary outcome variable. Like most efficacy studies for lubricating eye solutions, assessing improvement in patient-reported symptoms compared to reference products is the primary objective of this study. [36]

Due to the differences in the presentation of Humylub Ofteno® PF with one of its comparators, Hyabak®, and thanks to the characteristics of its bottles, this will be an open-label study.

Finally, considering the evaluation of the secondary variable of TRL efficacy by means of a non-invasive method, and since the equipment required to carry out this assessment is not so widely disseminated in ophthalmological offices and clinics in general, multiple research centers will be in charge of executing this study.

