7.3 Randomization

Randomization of subjects will be carried out using a computer-based assignment system. After signing the FCI, the patient will receive a patient number with which all their information will be encrypted pseudonymity during collection and completely anonymized during analysis.

The containers will be identified by means of labels, which, in accordance with current and applicable regulations, must contain at least:

1. Sponsor's name, address, and phone number.
2. Dosage form and route of administration.
3. Batch number.
4. Legend "For clinical studies only"
5. Expiration date.

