10.1.5 Patients included in the analysis

Those patients who meet an adherence $\geq 65\%$ of the expected weight of the PI and $\geq 80\%$ of expected applications in the patient's diary, will be included in the statistical analysis to meet the objective of the study. If it is not possible to assess the weight of the IP, only the patient's diary will be considered.

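### The replacement clause has no allocation rule, cap, deadline or masking, so one known arm could be refilled in an open-label trial; the power gained is small unless losses are heavy

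*Combined protocol and SAP*

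**What the plan says.** Section 10.1.4 states that "50 evaluable patients are required per arm". If that is missed because of "a loss of patients greater than 20% contemplated in this protocol (loss of follow-up or withdrawal of ICF"), then "the sponsor may replace these patients". Of the patients who left it adds: "The results obtained from the replaced patients will continue to be used for safety analysis and will be part of the ITT".

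Other sections bear on how this would work:

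- **Allocation.** Section 7.3: "Randomization of subjects will be carried out using a computer-based assignment system". It has no provision for replacements. Section 5.2 has replacement in its title but lists only reasons for removal.
- **Blinding.** Section 4.1 describes the trial as "Phase IV non-inferiority, controlled, open-label, comparative, multicenter clinical study", and section 4.2 gives the reason (differences in presentation and bottle).
- **Who analyses.** Section 10.1.1 gives the analysis to the sponsor's own personnel.
- **Efficacy set.** Under section 10.1.5, patients who reach the bottle-weight and diary adherence thresholds "will be included in the statistical analysis to meet the objective of the study".
- **ITT.** Sections 10.1.2 and 10.1.3 give this population a role only for adverse events and safety.
- **Tolerated loss.** Section 5.6 treats a loss below 20% as harmless to validity.

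**The concern.** The target is counted arm by arm. When one arm is short, the most direct way to restore it is to enrol patients into that arm. In an open-label trial the product would then be known before the patient is chosen, and the patient would join later in calendar time than those being replaced. The primary outcome is the patient-reported OSDI score, so knowledge of the product at selection matters.

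The choice is optional and belongs to the sponsor, who also analyses the data. No cap, closing date or masking to results by arm is given. Section 11.3 lists achievement of the primary objective and futility among the grounds for early termination. Either could be judged only by looking at results, and no rules for such looks are given.

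Retaining replaced patients in the ITT does not protect the efficacy comparison, because no efficacy analysis is assigned to that population. In the efficacy tables, patients who left would give way to newly selected ones. If leavers on one product had done badly, this could draw the arms together, which in a non-inferiority trial favours the claim.

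**Working it through.** **1. Trigger against target.** Planned: 60 per arm (section 10.2). A 20% loss is 0.20 × 60 = 12, leaving 48. A loss greater than 20% means 13 or more, leaving 47 or fewer. Keeping 50 allows a loss of only 10/60 = 16.7%. An arm with 48 or 49 evaluable therefore misses the target without triggering replacement. The cause is that 60 was obtained as 50 × 1.2, whereas 50/(1 − 0.2) = 62.5, or 63.

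**2. The plan's figure of 50.** Section 10.2.2 gives one-sided α = 0.05 (its formula uses z at 1 − α), power 80%, margin 10 points and a test-arm rate of 30%. The comparator rate is not stated. Assuming 30% there too:

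n = (0.30 × 0.70 + 0.30 × 0.70) × ((1.645 + 0.842)/0.10)² = 259.7, so 260 per arm.

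The 50 is not reproduced at equal rates. With 30% in the test arm and the margin as an allowed deficit, it needs a comparator rate of about 18.8%. I therefore show power on two premises.

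**3. Premise A: 50 per arm gives 80%.** The standardised distance at 50 per arm is 1.645 + 0.842 = 2.486 (unrounded z-values).

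- Both compared arms at n: power = Φ(2.486 × √(n/50) − 1.645).
- One arm at n, the other at 50, equal variances: power = Φ(2.486 × √[(2/50)/(1/n + 1/50)] − 1.645).

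Examples: for both arms at 47, Φ(2.410 − 1.645) = 77.8%. For one arm at 40, Φ(2.344 − 1.645) = 75.8%.

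| Left in the short arm(s) | One arm short: power | Gain from refilling to 50 | Both short: power | Gain from refilling to 50 |
|---|---|---|---|---|
| 47 (first value that triggers) | 78.9% | 1.1 | 77.8% | 2.2 |
| 40 | 75.8% | 4.2 | 71.9% | 8.1 |
| 30 | 69.4% | 10.6 | 61.1% | 18.9 |

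Refilling from 40 means ten replacements, 10/50 = 20% of the refilled arm.

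**4. Premise B: 30% in both arms.** Power = Φ(0.10/√(0.42/n) − 1.645), both compared arms at n.

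- n = 50: Φ(1.091 − 1.645) = 29.0%
- n = 47: 27.9% (refilling gains 1.1 points)
- n = 40: 25.2% (gains 3.8)
- n = 30: 21.2% (gains 7.8)

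These figures are for each pairwise comparison and count every retained patient as evaluable. Exclusions for poor adherence would lower the numbers further.

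**The case against.** The strongest defence is that section 7.3 provides for computer randomisation of subjects and exempts nobody. If replacements pass through that system like anyone else, allocation stays random. A reader might infer from the per-arm target that replacements must enter the short arm and that the randomised comparison is therefore broken. The documents do not say so. What stands is that they do not rule it out, and that newly randomising a replacement would not reliably refill the arm that is short.

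Second, the discretion is conditional. It needs a shortfall caused by losses above 20%, so 48 of 60 does not open it. That is correct, but once the condition is met nothing limits the number, the timing or what the decision-maker knows.

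Third, a reader might infer that replacement hides differential drop-out. That goes too far. Replaced patients stay in the safety population, section 5.6 asks for the reason for leaving, and losses by arm can be counted. The effect is confined to the efficacy analysis.

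Fourth, patients without a final evaluation, or with poor adherence, could be missing from the efficacy set even without replacement. That is true: the adherent-only set departs from the randomised comparison in any case. Replacement adds newly selected patients to it and restores the nominal count, without undoing bias from those who left.

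**Conclusion.** The point holds as a gap in the procedure. Section 10.1.4 permits a form of replacement that can break the randomised comparison, and nothing elsewhere closes it off. Whether it would do so depends on how replacements are allocated, which is not stated.

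A reader might also infer that replacement buys almost no power. That is right only near the trigger (1.1 to 2.2 points from 47, if 50 per arm gives 80%). From 40 the gain is 4.2 to 8.1 points and from 30 it is 10.6 to 18.9, and the clause sets no upper limit on the loss.

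The 80% premise is the sponsor's and is not reproduced at equal response rates. With 30% in both arms, an assumption for the comparators, 50 per arm has about 29% power, so refilling to 50 does not rescue the comparison. Separately, and on no assumption beyond the plan's own figures, the 20% trigger does not match the target of 50.

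**What to change.** Replace the clause in section 10.1.4 with wording such as:

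> Lost patients are not replaced one for one. Any additional patients are randomised 1:1:1 through the same computer system, under a rule based on overall losses only and fixed before any OSDI data by arm are seen. All originally randomised patients are kept in an all-randomised efficacy analysis, reported beside the adherent-patient analysis.

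The alternative is to delete the option, analyse the patients obtained and report the precision achieved.

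In either case, reconcile the loss allowance with the target, since a 20% loss from 60 leaves 48. Sections 10.1.4 and 10.2.1 should also agree on whether the evaluable number per arm is 50 or 60.

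The cost is wording, plus one further efficacy analysis that will need a stated method for missing final scores. With deletion, power is lost if losses are heavy: on the 80% premise, 4.2 to 8.1 points at 40 per arm and more below that. With 1:1:1 top-up, some added patients go to arms that are not short.

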10.1.5 Patients included in the analysis

Those patients who meet an adherence $\geq 65\%$ of the expected weight of the PI and $\geq 80\%$ of expected applications in the patient's diary, will be included in the statistical analysis to meet the objective of the study. If it is not possible to assess the weight of the IP, only the patient's diary will be considered.

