5.6 Procedure in case of loss of follow-up

For this protocol, loss of follow-up is defined as those patients who were randomized, who at some points were active patients in the study, but their final evaluation could not be completed.

If the participating patient does not attend their appointment, the research center must make a call to find out the reason and will attempt to make a new appointment within the established window period or an unscheduled appointment. In case it is not possible to make an appointment, the presence of AEs and the reason for leaving the study will be asked, as minimum data.

A follow-up loss of <20% is considered not to be a problem for the validity of the results obtained based on the sample size calculations. See point 10.2 Calculation of the sample size.

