7.5.1.2 Basal Visit

- Eligibility criteria: refers to the review by the PI, where it is found that the patient can be included in the study by meeting the inclusion criteria and not meeting the exclusion criteria.
- Evaluation of AEs: see section 7.4.4.1 Adverse events.
- TRLNI: see point 7.4.4.4 TRLNI.

- IP randomization: refers to determining the intervention that the patient will follow during the study. This assignment will be made at baseline visit (day 0). See point 7.3 Randomization
- Delivery of the PI and initiation of intervention refers to the delivery of the PI to the study patient, by the research center.
- Delivery of patient material and filling instructions refers to the delivery by the PI to the patient of the patient's diary, ID card and calendar improving adherence. The staff assigned by the research center will carry out prior training to the patient, on the completion of the diary.

7.5.1.3 Visit 1

- Evaluation of concomitant medications: see point 7.5.1.1 Screening Visit.
- Vital signs: refers to the measurement of heart rate, respiratory rate, systemic blood pressure and temperature. This information must be contained in the patient's medical history and the evolution notes of the patient's clinical file.
- OSDI: see section 7.4.4.2 OSDI score.
- CVAM: see section 7.4.4.3 Better corrected visual acuity.
- TRLNI: see point 7.4.4.4 TRLNI.
- Ocular surface stains: see points 7.4.4.5 Corneal and conjunctival staining with fluorescein and 7.4.4.6 Conjunctival staining with lysmine green.
- Comprehensive ophthalmological evaluation: see point 7.4.4.1 Adverse events.
- Evaluation of AEs: see section 7.4.4.1 Adverse events.
- Evaluation of adherence: see point 7.5.1.1 Scrutiny visit.

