10.1.2 Data Interpretation

The Kolmogorov-Smirnov and Shapiro Wilk tests will be performed, as applicable, to determine if the distribution of the data is normal in the results obtained in each study group [56].

The results of the continuous quantitative variables will be presented in measures of central tendency: mean, standard deviation, standard error and/or ranges.

- Intra-group analysis: For equal variances, Tukey's POST-HOC test will be used, otherwise the Dunnett statistic will be used. One-way analysis of variance (one-way ANOVA) will be used when applicable.
- Intergroup analysis: Differences between groups will be analyzed using the Repeated Measures Analysis of Variance (ANOVA) test or the Student's t-statistic when applicable.

A non-inferiority margin (δ) of 10% will be used for the primary efficacy endpoint, based on the primary endpoint of the study. The level of difference to consider significance will be an alpha (α) of 0.05 or less.

The result of the nominal and ordinal qualitative variables will be presented in frequencies, proportions and/or percentages.

The statistical analysis to identify significant differences in the qualitative variables will be carried out by creating 2x2 contingency tables and will be carried out as follows:

- Intra-group difference: McNemar test. This is applied to 2x2 contingency tables with a dichotomous feature, with pairs of paired subjects, to determine if the marginal frequencies of row and column are equal (marginal homogeneity) [7].

- Difference between groups: Pearson's X² (Chi-square) test or Fisher's exact test at expected values less than 5.

The level of difference to consider significance will be an alpha (α) of 0.05 or less.

For the reporting of adverse events, all subjects who were randomly assigned to an intervention group after baseline (intention-to-treat population, ITT) will be considered.

The final report of the results will be shown in tables or graphs, as appropriate.

Variable Type	Variable	A1	B1	B2	C1	D1	D2	D3	D4	E1	E2
Background											
A1	Demographic	DT									
Basal											
B1	Medical History/Selection Criteria	DT									
B2	Comprehensive ophthalmological evaluation	DT				TB	T	T	T	TB	TB
Efficiency											
C1	OSDI	DB			B					TB	
Secondary efficacy outcome											
D1	TRLNI				DB	B				TB	
D2	Corneal and conjunctival stains (TVL and TF)		DT	DT			TB			TB	
D3	Conjunctival Hyperemia		DT	DT		TB				TB	
D4	Chemosis		DT	DT		TB				TB	
Safety											

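### The primary objective is analysed only in patients who pass a post-randomisation adherence filter, with no all-randomised efficacy analysis and no rule for a missing OSDI visit score

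*Combined protocol and SAP*

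**What the plan says.** Section 10.1.5 is the only place that names who enters the efficacy analysis. Patients must reach both adherence thresholds (bottle weight at least 65%, diary at least 80%; diary alone if the weight cannot be assessed), and those patients "will be included in the statistical analysis to meet the objective of the study". Randomisation comes earlier; section 7.5.1.2 states "This assignment will be made at baseline visit (day 0".

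ITT appears in three places in section 10, and none of them assigns it an efficacy analysis:

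- Section 10.1.2: "For the reporting of adverse events, all subjects who were randomly assigned to an intervention group" are considered and labelled ITT.
- Section 10.1.3: the safety assessment covers patients "who have been exposed at least once to the intervention", also labelled ITT.
- Section 10.1.4: "The results obtained from the replaced patients will continue to be used for safety analysis and will be part of the ITT".

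Section 10.1.3 is titled as the missing-data procedure, but its only content is the safety-set sentence. Section 5.6 defines loss to follow-up as lacking a final evaluation. The centre first calls and tries to rebook; if that fails, "the presence of AEs and the reason for leaving the study will be asked, as minimum data". The same section regards losses below 20% as no threat to validity.

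Section 4.2 states that "this will be an open-label study", and the primary variable is the patient-completed OSDI (sections 7.4.1 and 7.4.4.2).

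**The concern.** Adherence can depend on the product received and on how well it works. A patient who finds the drops uncomfortable or unhelpful may use fewer of them and so leave the analysis. Withdrawal for intolerance of a study product (section 5.2) can have the same effect. A set selected in this way need not keep the balance that randomisation created, and knowledge of the assigned product gives both adherence and symptom reporting a further route to differ between arms.

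The direction cannot be predicted. If the test arm loses more poor responders than the comparator, the test product looks better than it is; if the comparator loses more, it looks worse. Since no other efficacy set is planned, nothing would show whether a non-inferiority result, or a failure to reach one, holds among all patients randomised.

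Two features add to this. The 20% allowance in section 10.1.4 counts only loss to follow-up and withdrawal of consent, so adherence exclusions are not budgeted. The sponsor also measures bottle weight (section 6.4) and runs the statistics (section 10.1.1), with no step that fixes the adherence classification before outcomes are seen by arm.

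**Working it through.** **What the diary threshold means.** Four applications a day for 30 days is 4 × 30 = 120. The threshold is 0.80 × 120 = 96, which is 96 / 4 = 24 days of full use. A patient who stops before about day 24 leaves the efficacy analysis.

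**The plan's own sample size.** The inflation in section 10.2.2 reproduces: 50 × 1.20 = 60 per arm, and 3 × 60 = 180. The 50 itself does not follow from the stated inputs: 30% in both arms, a 10-point margin, one-sided 0.05 and 80% power give 260 per arm, and the comparator rate is not stated. That is a separate matter; nothing below depends on it.

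**A bound that needs no response model.** If 10 of 60 patients per arm fall outside the analysed set, their unknown outcomes can move the all-randomised difference by up to 10/60 = 16.7 points either way. For example, 15/50 = 30% in both arms of the filtered set is compatible with 15/60 = 25.0% to 25/60 = 41.7% in each arm as randomised. The margin is 10 points.

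**Effect on the chance of a claim.** From the documents: 60 per arm, margin 0.10, one-sided alpha 0.05 (the formula in section 10.2.2 uses z at 1−α, 1.645), and a responder endpoint expected at 30% (sections 3.3 and 10.2.2). Assumed: one comparator, the exclusion fractions, how excluded patients respond, and a simple unpooled interval for the difference, because the plan names no non-inferiority interval.

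Let p be the true response rate in an arm, e the fraction excluded, and r the response of excluded patients relative to their arm (0 = none respond, 1 = same as the arm).

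- Rate in the analysed set: q = p(1 − e·r)/(1 − e), with n = 60(1 − e)
- SE = √[qA(1−qA)/nA + qB(1−qB)/nB]
- P(claim) = Φ((qA − qB + 0.10)/SE − 1.645)

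Worked case, p = 0.20 vs 0.30, e = 0.20 vs 0.05, r = 0: qA = 0.20/0.80 = 0.250 with n = 48; qB = 0.30/0.95 = 0.316 with n = 57; difference −0.066; SE = 0.0877; P = Φ(0.0342/0.0877 − 1.645) = 0.105.

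True rates exactly at the margin (20% test, 30% comparator), so any claim is false:

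| Excluded, test vs comparator | r | Difference in analysed set (points) | Chance of a false claim |
|---|---|---|---|
| 0% vs 0% | – | −10.0 | 5.0% |
| 10% vs 5% | 0 | −9.4 | 5.8% |
| 20% vs 5% | 0 | −6.6 | 10.5% |
| 25% vs 5% | 0 | −4.9 | 14.0% |
| 20% vs 5% | 0.5 | −8.3 | 7.4% |
| 20% vs 20% | 0 | −12.5 | 2.8% |
| 5% vs 20% | 0 | −16.4 | 0.9% |
| any | 1 | −10.0 | no bias |

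True rates equal at 30%, so a claim is correct, r = 0: 33% with no exclusion, 45% with 15% vs 5% excluded, and 17% with 5% vs 15%.

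Exact binomial enumeration of the same interval agrees within about 1.5 percentage points wherever it was checked.

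**The case against.** The strongest objection is that the larger figures need strong assumptions: an exclusion imbalance of 15 to 20 points, and every excluded patient a non-responder. The documents support neither, and all arms follow the same four-times-daily schedule. Milder cases hardly move: 10% vs 5% gives 5.8% (5.4% at r = 0.5), and 15% vs 10% gives 5.2%. Equal exclusion is conservative. The objective also names two comparators. If a claim needs both, and both are at the margin, simulation gives about 1.0% with no exclusion, 3.8% when 20% of the test arm and 5% of each comparator are excluded, and 5.3% at 25% against 5%. This stands: 10.5% and 14.0% are upper-end illustrations, not expected values. They are approached when one comparator is at the margin and the other is easily met.

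The interval is also assumed. Sections 7.4.4 and 10.1.2 list ANOVA for OSDI as a score, and the responder comparison comes from sections 3.3 and 10.2.2. That limits the precision of the figures but does not affect the selection problem.

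On the text, three qualifications are fair. Unanswered OSDI items are handled, because the score divides by the number answered (section 7.4.4.2), so the gap concerns a missing visit score. Section 10.1.4 may mean that an ITT set was intended for more than safety, but no efficacy analysis uses it. The two ITT definitions should nearly coincide, since product is handed over at the randomisation visit, so reconciling them is tidying rather than the core of the point.

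Finally, adherent-set analysis is accepted practice in non-inferiority trials. That is right, and it is a reason to keep the set, not to rely on it alone.

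**Conclusion.** The concern holds. The only efficacy set is selected on post-randomisation behaviour in an open-label trial with a patient-reported endpoint. The plan has no all-randomised efficacy analysis and no rule for a missing OSDI visit score.

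The size of the bias is unknown, because it depends on exclusion rates and on the response of excluded patients, which the documents do not give. Under the stated assumptions for a single comparator, the false-claim chance at the margin ranges from 0.9% to 14.0% against a nominal 5%, and is unchanged if exclusion is unrelated to response. The conclusion rests on the missing analysis, not on any one of these figures: as planned, a selection effect in either direction would go undetected.

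**What to change.** 1. In section 10.1.5, add an analysis of the primary endpoint in all randomised patients, in the arm assigned, including patients later replaced. Keep the adherent set as a co-analysis and claim non-inferiority only if both agree.
2. Use one ITT definition, all randomised, in sections 10.1.2, 10.1.3 and 10.1.4.
3. In section 10.1.3, pre-specify how a missing final OSDI is handled, for example multiple imputation by arm using baseline and Visit 1 OSDI. Use non-response imputation only as a sensitivity analysis, because it can dilute a true difference. With 20% missing at random in each arm, 20% vs 30% becomes 0.8 × 20% = 16% vs 0.8 × 30% = 24%, a difference of −8 points and an 8.5% chance of a false claim.
4. Fix and document each patient's adherence classification before outcomes are seen by arm.

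Adding the all-randomised analysis and the missing-score rule is the necessary repair; the agreement requirement and the choice of multiple imputation are reasonable options among several.

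The cost is revised wording, a second run of the primary analysis, programming of the imputation and a documented classification lock. No new patients or visits are needed. Patients lost to follow-up will still lack a final OSDI, so for them the result rests on imputation. Requiring both sets to agree lowers the chance of a positive claim; the loss is expected to be small but has not been calculated.
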